5.2. Breaking the Blind

At the initiation of the trial, the sites will be instructed on the method for breaking the blind. The method will be an electronic process via IVRS. Blinding codes should only be broken in emergency situations for reasons of subject safety (ie, when the unblinding information is considered clinically necessary for appropriate subject management). Whenever possible, the Investigator or sub-Investigator should consult with a member of the Sponsor study team prior to breaking the blind. When the blinding code is broken, the reason must be fully documented and entered in the source documents.

090177e1848ce2dd\Approved\Approved On: 23-Sep-2013 15:48

Phase A of this trial is subject-, Investigator-, and sponsor-blinded. Following completion of Phase A (defined as database lock), treatment assignment for subjects in Phase A of the trial will become available to limited staff from Pfizer/Merck and their delegates to permit authoring of the clinical study report. Phase B of the trial will be blinded to the subject, Investigator, and Sponsor or Sponsor-designate personnel responsible for study monitoring activities (including all site monitoring activities).

5.3. Drug Supplies

5.3.1. Formulation and Packaging

Ertugliflozin 5 mg, ertugliflozin 10 mg, and matching placebos will be supplied as immediate-release tablets for oral administration in Phases A and B. Tablets will be packaged into bottles or blister cards.

Pfizer will provide Investigator sites with sufficient amounts of blinded investigational product to accommodate expected recruitment. Blinded investigational product will be assigned to subjects via an IVRS or equivalent.

All investigational product containers dispensed to subjects should be returned to the Investigator site at the next clinic visit for the assessment of subject compliance and drug accountability.

5.3.2. Placebo Run-in

A single-blind placebo run-in will be administered starting at Day -14/Visit S3 where subjects will be instructed to take 1 tablet of placebo ertugliflozin 5 mg and 1 tablet of placebo ertugliflozin 10 mg each day from the bottles or blister card(s) provided for this period. The last dose of placebo run-in investigational product should be taken on the day prior to Day 1. Subjects should not be informed that they are taking placebo during this period. Subjects who are <80% compliant based on pill count with the Placebo Run-in medication will be ineligible for randomization.

5.3.3. Concomitant Metformin

Subjects will use the background metformin prescribed by their physician and provided in the local commercial packaging. Immediate Release (IR) and Extended Release (ER) forms are allowed in the study, provided that the same subject remains on the same formulation (IR or ER) from S2 to the Week 104 visit.

Metformin titration will be required for some subjects between Screening Visit 2 (S2) and Screening Visit 3 (S3), prior to the placebo run-in period. This will occur in subjects who have been receiving metformin monotherapy at a dose <1500 mg/day at S1 or who have been receiving metformin at a dose <1500 mg/day plus another AHA at S1.

The metformin dose should generally be increased by 500 mg per week (or as standard practice per the Investigator) to achieve the maximally approved/tolerated dose referring to the label, which must be ≥ 1500 mg/day. Metformin should generally be taken with meals.

090177e1848ce2dd\Approved\Approved On: 23-Sep-2013 15:48

Those subjects will enter the placebo run-in period at S3 after the metformin monotherapy dose of ≥ 1500 mg/day has been kept stable for at least 8 weeks.

The metformin dose will not be changed from Screening Visit 3 until the end of the trial (V15), except if medically necessary. In that case, all efforts should be made to get the subject back to the previous dose.

5.3.4. Administration (Ertugliflozin/Placebo)

On Day 1, each subject will be randomly assigned to ertugliflozin 5 mg, ertugliflozin 15 mg, or placebo.

The trial utilizes a double-dummy approach to maintain double-blinding, with a placebo tablet matching the ertugliflozin 5 mg tablet and another placebo tablet matching the ertugliflozin 10 mg tablet. Subjects will be dispensed 2 bottles or blister cards and given clear dosing instructions. They will be instructed to take 2 tablets per day of ertugliflozin/placebo, one from each bottle or blister card. Subjects randomized to ertugliflozin 5 mg will receive 1 ertugliflozin 5 mg tablet and 1 placebo ertugliflozin 10 mg tablet per day. Subjects randomized to ertugliflozin 15 mg will receive 1 ertugliflozin 5 mg tablet and 1 ertugliflozin 10 mg tablet per day. Subjects randomized to placebo will receive 1 placebo ertugliflozin 5 mg tablet and 1 placebo ertugliflozin 10 mg tablet per day.

The investigational product should be taken orally at approximately the same time of day in the morning from Day 1 through to Week 104 or early termination. In addition, subjects will be instructed to delay the self-administration of investigational product on the day of their visits, when the visit assessments should be completed prior to administration.

If a subject misses a dose of investigational product during the trial, he/she should be instructed to take it as soon as the subject remembers unless it is time for the next dose. Subjects should be instructed not to "make up" for the missed dose by taking two doses at the same time.

5.3.5. Drug Supplies for Phase B

The Sponsor will supply blinded glimepiride and matching placebo for glimepiride, for oral administration, as 1 mg and 2 mg strength over-encapsulated tablets or matching placebo.

Blinded glimepiride and matching placebo for glimepiride will only be provided to subjects who **were not** rescued in Phase A with open-label glimepiride. At entry into Phase B, **non-rescued** subjects in the placebo treatment group will receive blinded glimepiride in addition to placebo for ertugliflozin while **non-rescued** subjects in the ertugliflozin groups will receive a matching placebo for glimepiride.

Glimepiride/placebo will be supplied in bottles for dispensing at each visit containing sufficient supplies to permit dosing until the next scheduled visit. Glimepiride/placebo should be stored in accordance with the label. All blinded glimepiride and matching placebo for glimepiride containers dispensed to subjects should be returned to the Investigator site at the next clinic visit for the assessment of subject compliance and drug accountability.

5.3.5.1. Administration of Glimepiride/Matching Placebo

The dose of glimepiride/matching placebo will be initiated at 1 mg/day (or matching placebo for 1 mg tablet) starting on the day of the Week 26 visit for subjects who were not rescued in Phase A, and only if subject's fasting fingerstick glucose (FFSG) at Week 26 visit is ≥ 110 mg/dL (6.1 mmol/L).

If the subject's FFSG at Week 26 visit is < 110 mg/dL (6.1 mmol/L), the subject will not receive glimepiride/matching placebo at the Week 26 visit.

All subjects will continue with investigational product (ertugliflozin/placebo) during Phase B, regardless of whether a subject does or does not initiate glimepiride/matching placebo at Week 26.

For subjects started on glimepiride/matching placebo 1 mg at Week 26, at the Week 30 visit, the dose of glimepiride/matching placebo will be increased to 2 mg once daily (QD), if deemed appropriate by the Investigator based on the subject's self-monitoring blood glucose measurements and assessment of risk of hypoglycemia. Assessment of glimepiride dosing will then take place at subsequent clinic visits (ie, Weeks 39, 52, 65, 78, and 91). Further up-titration of glimepiride will be made in increments of 2 mg/day, with the maximum dose (6 or 8 mg QD) based upon the local label of glimepiride. Subjects may remain on 1 mg/day if appropriate based on finger-stick glucose monitoring.

Subjects who did not have glimepiride/matching placebo initiated at the Week 26 visit may have glimepiride/matching placebo initiated (with 1 mg dose) at any subsequent visit, if their FFSG is no longer < 110 mg/dL (6.1 mmol/L), and subsequently uptitrated, as described above. Down-titration is allowed at any time during the trial, as needed, in order to avoid hypoglycemia.

It is recommended that the dose of glimepiride be administered with breakfast or the first main meal of the day.

If any adjustment in the administration of glimepiride/matching placebo is necessary between scheduled visits, an unscheduled visit to the site should be performed.

In case of hypoglycemia:

If a subject experiences episodes of unexplained hypoglycemia (ie, not explained by missed meals or excess physical activity), the subject's glimepiride/matching placebo should be down-titrated to a dose determined appropriate by the Investigator. In general, glimepiride should be down-titrated by 2 mg/day (eg, 6 mg to 4 mg or 4 mg to 2 mg), or more rapidly, as considered appropriate by the Investigator. In subjects receiving 2 mg/day the dose should be reduced to 1 mg/day in case of hypoglycemia. Subjects on glimepiride/matching placebo 1 mg who experience unexplained hypoglycemia should interrupt glimepiride/matching placebo and may continue in the trial off of glimepiride/matching placebo. If unexplained hypoglycemia continues to occur after glimepiride/matching placebo is interrupted, the subject should be considered for discontinuation from the blinded investigational product

according to [Section 6.7.2](#) – Reason for Discontinuation from Investigational Product or From the Study.

If a subject has had glimepiride/matching placebo interrupted or down-titrated, and re-initiation or up-titration of therapy is considered appropriate, then re-initiation and/or up-titration of glimepiride/matching placebo may be performed through the end of Phase B according to the guidelines used for initial up-titration.

Note: If glimepiride/matching placebo is re-initiated, the dose should not be up-titrated beyond the dose at which hypoglycemia originally occurred.

5.3.6. Compliance

Subjects will be directed to bring any used and unused bottles or blister cards to each visit. The Investigator must maintain a complete and current accountability record for the investigational product.

Compliance with the placebo run-in medication should be monitored by study personnel at the site, at the end of the placebo run-in (Day 1/Visit 4), by comparing the returned investigational product with the amount dispensed and the information reported by the subject. The number of tablets issued minus the number of tablets returned will be used to calculate tablets taken. From this information, compliance will be calculated as:

Compliance = $100 \times (\text{tablets dispensed} - \text{tablets returned}) / \text{No. of days between visits} \times \text{No. of tablets taken per day}$

Subjects who are <80% compliant based on pill count with the Placebo Run-in medication are ineligible for randomization.

During the remainder of the trial, compliance for subjects must be assessed for the ertugliflozin/matching placebo, and blinded glimepiride/placebo therapy (if applicable) by taking the subject's report.

The Investigator or designee will counsel subjects who report taking <80% of the prescribed medication (s) described above following randomization. The Investigator or designee will determine factors that resulted in <80% compliance with these medication(s) and will take steps to improve compliance. Subjects will continue these medications but will be counseled on the importance of taking their medication(s) as prescribed. Subject counseling will be documented in source documents.

5.4. Drug Storage and Drug Accountability

The blinded investigational product dispensing and accountability will be managed by IVRS and monitored by clinical research associates (CRAs) in addition to the investigational product inventory monitoring at each site. The Investigator, or an approved representative, eg, pharmacist, will ensure that all medication is stored in a secured area, under recommended storage conditions, and in accordance with the drug label and applicable regulatory requirements.

090177e1848ce2dd\Approved\Approved On: 23-Sep-2013 15:48

Storage conditions stated in the SRSD [Investigator Brochure's (IB)] will be superseded by the label storage.

The Investigator must maintain adequate records documenting the receipt, use, loss, or other disposition of the investigational product(s). Pfizer or its designee may supply drug accountability forms that must be used or may approve use of standard institution forms.

At the end of the trial, Pfizer or its designee will provide instructions as to disposition of any unused investigational product. If Pfizer or its designee authorizes destruction at the study site, the Investigator must ensure that the materials are destroyed in compliance with applicable environmental regulations, institutional policy, and any special instructions provided by Pfizer or its designee. Destruction must be adequately documented.

5.5. Concomitant Medication(s)

All AHAs taken by the subject at any time prior to S1, and any other medications taken within 8 weeks prior to S1, will be recorded on the appropriate electronic case report form (eCRF). The site may rely on subject report for this information. Concomitant medications taken during the trial must also be recorded. All subjects must be questioned about concomitant medication according to the [Schedule of Activities](#).

Medications that are indicated as prohibited in the Exclusion Criteria must not be used prior to or during the trial as specified in [Section 4.2](#).

Subjects who are not on a stable dose of blood pressure or lipid altering medications at S1 can be scheduled appropriately for S3 and Day 1 to ensure they have a stable dose for at least 4 weeks prior to randomization per exclusion criterion 25. To the extent that is reasonable, the Investigator should make all efforts to modify these regimens in advance of randomization to avoid the need to change after randomization. However, the Investigator or subject's physician/health care provider is permitted to make adjustments in blood pressure or lipid altering background therapy throughout the trial if clinically warranted.

Subjects who are receiving calcium supplementation upon entry into the trial should continue to receive these medications at the same doses throughout the trial. The concentration of 25-hydroxyvitamin D will be measured at S3. Based on the results, the Investigator will be allowed to supplement subjects with vitamin D according to local practices or country dietary guidelines and if clinically necessary.

Initiation of a weight-loss medication during the study (eg, orlistat, phentermine, topiramate, lorcaserin) is prohibited. **Note:** Subjects who are on treatment with a weight-loss medication or other medication associated with weight changes (eg, anti-psychotic agents) and who are weight-stable (ie, <5% change in body weight within 6 months of S1) are eligible to participate in the study and permitted to continue these medications during the study.

5.6. Glycemic Rescue Therapy

Subjects will be prescribed open-label glycemic rescue therapy and dosed according to physician judgment, if they meet specific, progressively more stringent, glycemic thresholds based on a **repeated, confirmed** FPG or HbA1c measured by the **central lab** according to the directions below:

Table 4. Glycemic Thresholds

| | |
|--------------------------------|---|
| Randomization through Week 6: | FPG >270 mg/dL (15.0 mmol/L) |
| After Week 6 through Week 12: | FPG >240 mg/dL (13.3 mmol/L) |
| After Week 12 through Week 26: | FPG >200 mg/dL (11.1 mmol/L) |
| After Week 26: | FPG >200 mg/dL (11.1 mmol/L) or HbA1c >8.0% (64 mmol/mol) |

Subjects who meet the glycemic rescue thresholds detailed in Table 4 should have the repeat FPG measurement performed as early as possible (within 7 days following the receipt of test results).

During Phase A, subjects exceeding pre-specified glycemic thresholds after randomization will have glycemic rescue therapy initiated with open-label glimepiride. Glycemic rescue therapy must be initiated at a rescue visit which is either a scheduled or an unscheduled visit at the investigational site, and not by a telephone visit. Dosing will be at the Investigator's discretion and the Investigator will be responsible for managing the initiation and titration of the glimepiride rescue therapy according to the country-specific product label. At the rescue visit, immediately prior to initiation of glycemic rescue therapy, subjects meeting rescue criteria must undergo the procedures described in [Section 6.6](#).

Subjects requiring glycemic rescue therapy during Phase A and entering into Phase B are to remain in the trial up to the end, and will continue to receive investigational product (ertugliflozin/placebo) in a blinded fashion as well as open-label glimepiride. These subjects will not receive blinded glimepiride/placebo therapy during Phase B.

Additional glycemic rescue therapy with basal insulin should be initiated as follows:

During Phase A (prior to Week 26 visit):

- *Subjects who were initiated on open-label glimepiride rescue therapy, and who reached the maximum allowed dose (or tolerated dose, if lower), who meet glycemic rescue FPG criteria (after at least 2 weeks on maximum dose of glimepiride), will have basal insulin initiated and managed as considered appropriate by the investigator (ie, including selection of agent and starting dose, timing of administration, and uptitration).*

During Phase B:

- *Subjects who were initiated on open-label glimepiride rescue therapy in Phase A, who meet glycemic rescue criteria after at least 2 weeks on maximum dose of*

open-label glimepiride for FPG criteria or at least 8 weeks for HbA1c criteria, will have basal insulin initiated and managed as considered appropriate by the investigator (ie, including selection of agent and starting dose, timing of administration, and up-titration).

- *Subjects not on Phase A open-label glimepiride rescue therapy* who meet glycemic rescue criteria after at least 2 weeks on maximum dose of blinded glimepiride or matching placebo for FPG criteria or at least 8 weeks for HbA1c criteria will have basal insulin initiated and managed as considered appropriate by the investigator (ie, including selection of agent and starting dose, timing of administration, and up-titration).

Basal insulin must be initiated at a rescue visit which is either a scheduled or an unscheduled visit at the investigational site, and not by a telephone visit. Consideration should be given to reducing the dose of glimepiride (either open-label, for rescued subjects, or blinded glimepiride or matching placebo, for non-rescued subjects) as basal insulin treatment is initiated and up-titrated.

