Note: subjects whose Week 26 visit fasting fingerstick glucose is <110 mg/dL (6.1 mmol/L) will **not** have the glimepiride or matching placebo initiated at the Week 26 visit. At each subsequent scheduled study visit, if the fasting fingerstick glucose (FFSG) is \geq 110 mg/dL, glimepiride or matching placebo tablets may be initiated (unless not considered appropriate by the investigator based upon the risk of hypoglycemia).

During Phase B, glycemic rescue therapy with basal insulin should be initiated in subjects with glucose values or HbA1c values exceed protocol-specified values (See [Section 5.6](#))

The trial is designed to evaluate the efficacy, safety and tolerability of the 5 mg and 15 mg oral doses of ertugliflozin on glycemic control, body weight, and blood pressure following a 26-week dosing period in adult subjects with T2DM and inadequate glycemic control on metformin monotherapy. It is also designed to evaluate the longer-term efficacy, safety and tolerability of ertugliflozin during the entire 104-week treatment period, which includes a 78-week double-blind extension period. A key purpose of this 78-week extension period is

090177e1848ce2ddApproved\Approved On: 23-Sep-2013 15:48

to collect additional safety data of ertugliflozin on BMD. The effect of ertugliflozin on BMD will be assessed by DXA. All DXA data throughout the trial will be forwarded to a central evaluation facility to ensure standardization.

Approximately 600 subjects will be randomized to ensure a minimum of 480 subjects (160 per arm) will provide HbA1c data at the Week 26 primary timepoint. Given the plans not to replace those subjects who are withdrawn early, the 600 subjects randomized will also account for an approximate 20% premature withdrawal rate for HbA1c data to allow for withdrawn subjects who will still be included in the analysis, but will not necessarily have Week 26 data available.

Glycemic Rescue Therapy:

Subjects will be prescribed rescue therapy in the form of open-label glimepiride and basal insulin, and dosed according to Investigator judgment, if they meet specific glycemic criteria which become progressively more stringent throughout the trial. Provision of rescue with basal insulin is to occur only once subjects have first been titrated to a maximum tolerated or maximum approved dose of glimepiride (based on local country label) and continue to exceed the protocol-specified glycemic values.

Endpoints:

Primary Endpoint:

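### Both Phase B basal-insulin bullets in Section 5.6 omit the tolerated-dose alternative that the Phase A bullet and the synopsis provide

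*Combined protocol and SAP*

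**What the plan says.** Section 5.6 governs when basal insulin is added to glimepiride.

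- **Phase A bullet.** It covers subjects on open-label rescue "who reached the maximum allowed dose (or tolerated dose, if lower". It then gives the waiting time as "after at least 2 weeks on maximum dose of glimepiride".
- **Phase B, first bullet** (rescued in Phase A). It asks for at least 2 weeks (FPG) or 8 weeks (HbA1c) on the maximum dose of open-label glimepiride.
- **Phase B, second bullet** (not on Phase A open-label rescue). Insulin starts "after at least 2 weeks on maximum dose of blinded glimepiride or matching placebo for FPG criteria", or after at least 8 weeks for HbA1c.

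The thresholds after Week 26 (Table 4) are a confirmed FPG above 200 mg/dL or HbA1c above 8.0%.

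The synopsis paragraph on rescue states one rule without limiting it to a phase: insulin comes "only once subjects have first been titrated to a maximum tolerated or maximum approved dose of glimepiride".

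Section 5.3.5.1 sets the titration rules for the blinded supply. Up-titration proceeds "with the maximum dose (6 or 8 mg QD) based upon the local label of glimepiride". It also provides that "Down-titration is allowed at any time during the trial, as needed, in order to avoid hypoglycemia". A subject with unexplained hypoglycemia on 1 mg "should interrupt glimepiride/matching placebo and may continue in the trial off of glimepiride/matching placebo". If the drug is re-initiated, "the dose should not be up-titrated beyond the dose at which hypoglycemia originally occurred".

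**The concern.** In the Phase A bullet the tolerated-dose wording comes first, so the later mention of maximum dose can borrow its meaning. The Phase B bullets have no such wording to borrow from. For the blinded supply, the only place that puts a figure on the term is Section 5.3.5.1, and there it means the label ceiling. A site reading the two sections together could reasonably conclude that 6 or 8 mg must be reached before insulin is allowed.

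That matters for a subject whose hypoglycemia has fixed the dose below the ceiling or ended it. If that subject later has confirmed rescue-level hyperglycemia, the literal rule never opens. The other exits are poor:

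- The hyperglycemia discontinuation criterion in Section 6.7.2 presupposes that insulin has already been adjusted as far as possible, or that the subject has declined it.
- Exclusion criterion 30 in Section 4.2 bars insulin except for short hospital use or as glycemic rescue.
- What remains is stopping investigational product, either for needing a prohibited medication or on the investigator's judgment (criteria 5 and 8 of Section 6.7.2).

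A rescue could therefore be delayed or turned into a discontinuation. Incidence of rescue and time to rescue up to Weeks 52 and 104 are listed secondary endpoints (Section 2.2.2), so differing site readings could also enter those data.

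**Working it through.** The plan gives no figure to reproduce, and the point depends on no sample size, power or rate. The check is a comparison of texts.

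**Step 1: the dose condition in each place.**

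| Place | Subjects | Dose condition for insulin | Tolerated-dose alternative |
|---|---|---|---|
| Synopsis, Glycemic Rescue Therapy | not limited by phase | tolerated or approved maximum | yes, in equivalent words |
| 5.6, Phase A bullet | open-label rescue | allowed maximum, or tolerated if lower | yes |
| 5.6, Phase B bullet 1 | rescued in Phase A | maximum dose, open-label | no |
| 5.6, Phase B bullet 2 | not rescued in Phase A | maximum dose, blinded drug or placebo | no |
| Section 3, Phase B statement | all Phase B | none stated; refers to 5.6 | not applicable |

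**Step 2: what maximum dose means in Phase B.** Section 5.3.5.1 ties it to 6 or 8 mg once daily for the blinded supply, which is the supply named in bullet 2. For open-label glimepiride (bullet 1), Section 5.6 leaves titration to the investigator under the country label and gives no figure. The literal reading is therefore firmer for bullet 2 than for bullet 1.

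**Step 3: whether the protocol itself creates subjects who cannot reach that dose.** It does, in two ways under Section 5.3.5.1.

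- *Capped on re-initiation.* If hypoglycemia first occurred at 4 mg and the drug is later restarted, the dose may not exceed 4 mg. The shortfall is 6 − 4 = 2 mg against a 6 mg ceiling, or 8 − 4 = 4 mg against an 8 mg ceiling. On the literal text the 2-week and 8-week waits never begin.
- *Off the drug.* A subject who interrupts at 1 mg and continues without it is on no dose at all, so again no wait can begin.

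Down-titration alone does not create a permanent case, because Section 5.3.5.1 allows up-titration again through the end of Phase B.

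**Step 4: who is exposed.** Among subjects not rescued in Phase A, only the placebo arm takes active glimepiride (Sections 3 and 5.3.5). Dose-limiting hypoglycemia under bullet 2 would be expected mainly there. Bullet 1 subjects can come from any arm.

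**Step 5: reach into the analyses.** The Phase B bullets apply after the Week 26 visit, and the testing hierarchy in Section 9.2.2 is confined to Week 26. No hypothesis is tested at Week 52 or 104.

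**The case against.** The best reply is that the rule is already stated elsewhere. The synopsis is not limited to Phase A. Section 3 says insulin should be started in Phase B once the thresholds are passed, with no dose condition. The opening of Section 5.6 says that subjects meeting the thresholds will receive rescue. The Phase A bullet uses the bare term maximum dose as shorthand immediately after giving the tolerated-dose alternative, and the Phase B bullets follow directly and reuse it. They also say when insulin will be started; they do not say only then.

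Most of this stands as evidence of intent, and many investigators would rescue such a subject anyway. It does not remove the gap. Section 3 refers the reader to Section 5.6 for the operative rule. The synopsis rule sits in a paragraph on open-label glimepiride and basal insulin, so its reach to the blinded supply has to be inferred. The capped case is also narrow: it needs hypoglycemia, interruption, re-initiation and then confirmed hyperglycemia.

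A reader might infer three stronger points that the documents do not support.

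- **That the plan means to deny insulin to dose-limited subjects.** The synopsis says otherwise.
- **That a delay in weeks can be attached to the omission**, for example by supposing a subject reduced to 1 mg and held there to Week 104. Section 5.3.5.1 permits raising the dose again after a reduction, so any such figure would measure the supposition and not the plan.
- **That the between-arm comparison of rescue is biased by a known amount.** The tilt toward the comparator arm is plausible, but no rate in the documents sizes it.

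**Conclusion.** The point holds as a minor internal inconsistency. Both Phase B bullets omit an alternative that the Phase A bullet and the synopsis provide. Followed literally, they give no stated insulin route to a subject whom hypoglycemia has capped below the label ceiling or taken off the drug.

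This rests on reading maximum dose in the Phase B bullets as Section 5.3.5.1 uses it. That reading is reasonable for the blinded supply and less secure for open-label glimepiride.

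The size is limited to subjects who are both dose-limited and above FPG 200 mg/dL or HbA1c 8.0% in Phase B. The documents do not allow that number to be estimated. The consequence is mainly one of subject care, with a possible secondary effect on the Week 52 and Week 104 rescue endpoints. The Week 26 primary and secondary analyses are unaffected.

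**What to change.** In both Phase B bullets of Section 5.6, after maximum dose, insert: (or maximum tolerated dose, if lower). This brings them into line with the Phase A bullet and the synopsis.

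As a separate clarification, which goes beyond what those two texts now say, state that subjects who stopped glimepiride or matching placebo because of hypoglycemia qualify for basal insulin once the rescue threshold is confirmed. Without it, someone taking no drug has no dose on which a 2-week or 8-week wait could run.

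The cost is one phrase in two bullets and one added sentence. Endpoints, sample size, blinding, titration rules and analyses do not change.
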